7.3.2. Treatment satisfaction questionnaire for medication version 1.4

TSQM version 1.4 is a self-report questionnaire for investigating treatment satisfaction. TSQM version 1.4 is the original version created with domain scoring for effectiveness, convenience, global satisfaction, and side effects with 14 items. Then each domain is scored by formula. The formula for TSQM scoring will be stated in Statistical Analysis Plan. TSQM scores range from 0 to 100 by each domain, higher scores indicate that the patient is in a greater satisfaction.

7.3.3. EuroQoL-5 dimension-3 level index and EuroQoL-visual analogue scale

EuroQoL-5 dimension (EQ-5D) is a standardized measure of health status, such as quality of life. The EuroQoL-5 dimension-3 level (EQ-5D-3L) essentially consists of 2 pages – the EQ-5D descriptive system and EuroQoL-visual analogue scale (EQ-VAS).

The EQ-5D-3L descriptive system comprises the following 5 dimensions: mobility, self-care, usual activities, pain/discomfort and anxiety/depression. Each dimension has 3 levels: no problems, some problems, extreme problems. The respondent is asked to indicate his/her health state by ticking (or placing a cross) in the box against the most appropriate statement in each of the 5 dimensions.

The EQ VAS records the respondent's self-rated health on a vertical, visual analogue scale where the endpoints are labelled 'Best imaginable health state' and 'Worst imaginable health state'. This information can be used as a quantitative measure of health outcome as judged by the individual respondents. The scale is 0 to 100, higher scores imply that the patient is in a better health state.

The formula for EQ-5D scoring will be stated in Statistical Analysis Plan.

7.4. Data sources

Once a subject satisfies the inclusion criteria and voluntarily consents to participate in the study, subject data will be collected through review of medical records and patient questionnaires. Variables collected from the medical chart include demographic and clinical characteristics. Educational status, total income for the past year, and the current employment status will be collected from the questionnaires. Treatment satisfaction and the quality of life questions will be collected using the TSQM questionnaires and EQ-5D measurements, and the subject will self-record these.

7.5. Study sample size

The purpose of this study is to compare treatment satisfaction and quality of life in patients with RA who are receiving adalimumab or tofacitinib citrate. It is essential to identify the minimum sample size required to obtain statistically significant differences between the two groups. The equation below was used to calculate the sample size in this study [31].

$$N = \frac{2\sigma^2}{(\mu_1 - \mu_2)^2} [z_{1-\alpha/2} + z_{1-\beta}]^2$$

- σ : Standard deviation from the overall satisfaction pooled ≈ 14.58 (SD1: 16 [18], SD2: 13 [24])

$$\sigma = \sqrt{(\sigma_1^2 + \sigma_2^2)/2}$$

- μ_1 : Average of the overall satisfaction measured (larger) = 83 [24]
- μ_2 : Average of the overall satisfaction measured (smaller) = 79 [24]
- $z_{1-\alpha/2}$: 95% confidence interval (double-sided) significance = 1.96
- $z_{1-\beta}$: 80% power threshold = 0.842

Sample size was calculated based on literature that compared the median general satisfaction number between two drugs from the TSQM and the EQ-5D index score [24].

Jobanputra P et al. (2010) reported that the median EQ-5D index score and the median overall satisfaction score from TSQM (interquartile range) at 3 months after taking the medication in the adalimumab group were 0.62 (0.59–0.76) and 83 (67–100), respectively. In contrast, these scores were 0.62 (0.52–0.76) and 79 (58–92), respectively, in the etanercept group. Based on the sample number calculated in this study, we assumed that the average scores for the EQ-5D index or TSQM would be similar to the median scores from this measurement tool. This is because the interquartile ranges were almost symmetrical to the median value. We also assumed that the difference between the 3rd interquartile and median values (or the difference between the median and the 1st interquartile values) would replace the deviation from the general EQ-5D index or TSQM scores. This is because approximately 67% of the normal distribution data falls within the average \pm 1 standard deviation, whereas 50% of uniform distribution data falls within median \pm interquartile (in other words, within the interquartile range: Q1–Q3) values. Based on these assumptions, the standard deviations for the EQ-5D index scores were from 0.03 (= 0.62–0.59) to 0.14 (= 0.76–0.62) in adalimumab and from 0.1 (= 0.62–0.52) to 0.14 (= 0.76–0.62) in etanercept. Under the same assumption, the standard deviations for the TSQM scores were from 16 (= 83–67) to 17 (= 100–83) in adalimumab and from 13 (= 92–79) to 21 (= 79–58) in etanercept.

We assumed 0 (= 0.62–0.62) and 4 (= 83–79) points as the difference in the average EQ-5D and TSQM scores between patients receiving adalimumab and tofacitinib citrate. We also assumed the standard deviations as 0.03–0.14 and 16–17 points for the EQ-5D index and TSQM, respectively, in patients receiving adalimumab and in patients receiving tofacitinib citrate, the EQ-5D index and TSQM as 0.1–0.4 points and 13–21 points, respectively. Through various combinations of standard deviations, we assumed that the minimum pooled standard deviation is 0.07 ($= \sqrt{(0.03^2 + 0.1^2)/2}$) and 14.58 ($= \sqrt{(16^2 + 13^2)/2}$), and the maximum pooled standard deviation is 0.14 ($= \sqrt{(0.14^2 + 0.14^2)/2}$) and 19.1 ($= \sqrt{(17^2 + 21^2)/2}$) in the EQ-5D index and TSQM, respectively.

It was calculated that a total of 32 subjects in each group will be needed to detect the average difference of 0.05 points in EQ-5D with an 80% power at 5% significance, and a standard deviation of 0.07. The average difference of EQ-5D between the groups from a previous study was 0, which could not be used to calculate the sample size. Therefore, we voluntarily selected a small number, 0.05, as the average difference for the calculation. If 0.14 is used as the pooled standard deviation, a total of 125 per group will be needed.

When 14.58 is set as the pooled standard deviation for TSQM, a total of 209 subjects will be needed for each group for an 80% power with 5% significance. If 19.1 is set as the pooled standard deviation, a total of 359 subjects will be needed for each group.

Based on the above calculations of the range of sample sizes for each group, the most number needed for each group, conservatively, is 360 subjects. Considering 10–20% of subjects not consenting, the actual sample size would be 400–450 subjects per group. Therefore,

approximately 420 subjects will be identified from each group from the total of 840 subjects in this study.

Considering the geographic distribution and the number of patients as well as the clinical experiences and the academic success of the physicians, institutions participating in this study are deemed representative hospitals to care for patients with RA in Korea. Therefore, we believe that subjects who are screened from these institutions and undergo inclusion/exclusion criteria and the consent process are representative of Korea's patients with rheumatoid arthritis who either use tofacitinib citrate or adalimumab.

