#### 7.2.3.1 Propensity Score Matching

There are concerns of selection bias in the selection of the subject population in observational studies, and there are limitations in inferring correlations owing to the absence of randomization. Selection bias means there is a higher chance of subjects being assigned to a treatment arm based on a particular covariate, and this covariate can be a disturbing variable in establishing the difference between the treatment groups [37]. In order to balance the covariates between the groups, the propensity score method can be used. For example, a study by Bangalore et al. (2015) involved patients with polyvascular disease, and in this study, 1:1 matching was performed through propensity scores using demographic and clinical characteristics as matching variables to compare the mortality rate and risk ratio between CAGB and PCI groups. Although there was no significant difference in mortality rate, the PCI group had a higher risk of myocardial infarction than the CAGB group [38].

In this study, the difference in treatment satisfaction and quality of life scores between the two groups that have been matched by propensity score will be compared. Propensity scores will be calculated using subjects' demographic and clinical characteristics as covariates. Matching will be done using the greedy matching (nearest neighbor) method. Assuming the ratio of 2:1, the greedy matching method will randomly select one subject from treatment group 2 and set a range of propensity scores using treatment group 2 as the center through the caliper. Two subjects from treatment group 1 that have the closest propensity scores will be selected. In this case, the caliper will be determined after reviewing the data. If more than 25% of the standard group is eliminated after matching or if the distribution of covariates in the two groups are thought to be different, inverse probability of treatment weighting (IPTW) can be used for analysis.

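### The TSQM sample size uses median-to-quartile distances as standard deviations, so 80% power at a conservative 360 per group is not established

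*Protocol*

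**What the plan says.** Protocol 7.5, repeated in SAP 1.1.2, sizes the study with the two-sample normal formula at two-sided 5% and 80% power. The inputs come from a cited randomised comparison of adalimumab with etanercept, with etanercept standing in for tofacitinib. TSQM overall satisfaction there had median 83 (quartiles 67 and 100) on adalimumab and 79 (58 and 92) on etanercept.

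The plan treats medians as means, which gives a difference of 4 points. It assumes that a median-to-quartile distance "would replace the deviation from the general EQ-5D index or TSQM scores". The TSQM values are therefore 16 to 17 for adalimumab and 13 to 21 for the comparator, with pooled values from 14.58 to 19.1. The reason offered begins "This is because approximately 67% of the normal distribution data falls within the average" plus or minus one SD, and sets this against the 50% of uniform data that lie between the quartiles.

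The upper end sets the size: "If 19.1 is set as the pooled standard deviation, a total of 359 subjects will be needed for each group", and so "the most number needed for each group, conservatively, is 360 subjects". An allowance for 10–20% "of subjects not consenting, the actual sample size would be" 400–450 per group, and about 420 per group (840 in total) are to be identified.

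**The concern.** The quartiles enclose the middle 50% of a distribution, whereas one SD either side of a normal mean encloses about two thirds. A median-to-quartile distance is therefore shorter than the SD for normal data, and also for uniform data. The plan's own justification states the reason why the two differ, and it applies no scaling factor.

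Treatment satisfaction is the primary objective, and 360 per group rests only on the TSQM calculation, because the EQ-5D sizes are far smaller. If the SD is understated, the stated power is overstated. A non-significant TSQM result could then be read against an 80% power claim that the quoted figures do not support. What is at stake is the stated design property; no estimate, interval or test in the SAP depends on it.

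**Working it through.** **Inputs** (Protocol 7.5): difference 4 points; z-values 1.96 and 0.842, sum 2.802; TSQM quartiles 67/83/100 and 58/79/92, so the IQRs are 33 and 34. Protocol 7.3.2: "TSQM scores range from 0 to 100 by each domain".

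**1. Reproduce the plan.** n = 2·SD²/4² × 2.802².
- SD 14.58: 208.6, so 209.
- SD 19.1: 358.02, so 359.
- Non-consent: 360/0.9 = 400 and 360/0.8 = 450.

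All agree with the plan.

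**2. The SD that 360 can tolerate.** SD = (4/2.802)·√(n/2). At n = 360 this is 19.15.

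**3. What the quartile distance represents.** It is 0.6745 SD for normal data, so SD = IQR/1.349. For uniform data of width w, the distance is w/4 and the SD is w/√12, so the ratio is 0.866 and SD = 2·IQR/√12.

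**4. Power for 4 points with 360 analysed per group, unadjusted two-group comparison.** Power = Φ(4/(SD·√(2/360)) − 1.96). Detectable difference at 80% power = 2.802·SD·√(2/360).

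| Assumed shape | Pooled SD | n needed per group | Power at 360 | Detectable difference |
|---|---|---|---|---|
| Normal (24.5 and 25.2) | 24.8 | 606 | 58% | 5.2 |
| Uniform (19.05 and 19.63) | 19.3 | 368 | 79% | 4.0 |
| Normal as above, capped at 100 (19.5 and 20.9) | 20.2 | 402 | 76% | 4.2 |
| Even spread between quartiles, lowest score 0 | 27.3 | 733 | 50% | 5.7 |
| same, lowest score 20 | 22.7 | 507 | 66% | 4.7 |
| same, lowest score 33 | 19.9 | 389 | 77% | 4.2 |
| same, lowest score 40 | 18.4 | 334 | 83% | 3.8 |
| same, lowest score 50 | 16.5 | 267 | 90% | 3.4 |

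The last five rows put a quarter of the scores evenly between successive points: (lowest, 67, 83, 100, 100) for adalimumab and (lowest, 58, 79, 92, 100) for the comparator. The lowest score is my assumption; neither document gives one. In this family the pooled SD equals 19.15, and power reaches 80%, when the lowest score is about 36.5.

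The normal row cannot hold literally. It puts 1 − Φ(17/24.46) = 24% of adalimumab scores and 1 − Φ(21/25.20) = 20% of comparator scores above 100. The uniform row also runs past 100.

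**5. Non-consent.** 360/420 = 0.857, so 420 identified covers about 14%. At 20%, 420 × 0.8 = 336 remain. Power at SD 19.1 is then 77.5%, and 80% needs an SD of at most 18.5.

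**6. EQ-5D.** IQR/1.349 gives SDs of 0.126 and 0.178, pooled 0.154, which needs 150 per group for 0.05. Rescaling the plan's largest pooled value, 0.14/0.6745 = 0.208, needs 271. Both are below 360, so EQ-5D is still covered.

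**The case against.** Several points on the other side have weight.

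- **The plan names the uniform distribution, and it conditions each size on an SD.** Under a uniform shape 360 falls short by only 8 per group (368), with power 79%, and the plan shows a 209–359 range. This stands, and it limits the criticism to the SD rationale and the claim of conservatism. Even so, the shape that the plan mentions needs slightly more than 360.
- **The 58% case is impossible on a 0–100 scale.** This also stands. That figure is a normal-theory reference only and needs that label.
- **The bounded range depends on an assumed lowest score, and it keeps 4 points although those shapes imply other mean differences.** Applied consistently, the even-spread shapes give a difference of 5.25 and power of 73% to 99%; the capped normal gives 3.33 and 60%. Holding the plan's 4 points fixed answers a narrower question: power for 4 points. The movement in both directions adds to the uncertainty and does not rescue a single 80%.
- **If 420 per group were analysed,** power would be 85% (uniform) or 82% (capped normal), but 65% under normal theory. The plan, however, introduces the step from 360 to 420 as an allowance for non-consent.
- **Covariate adjustment may gain precision.** That is possible, while matching may lose subjects; SAP 7.2.3.1 sets a fallback "If more than 25% of the standard group is eliminated after matching". The net direction is unknown.
- **It is late to change power wording.** The SAP is dated 12 March 2020 and data collection ends on 31 March 2020. That is why only a wording change is proposed.

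**Conclusion.** The concern holds. The arithmetic is correct, but the SD input is not what it is said to be. The stated 80% power at 360 per group is conditional on a pooled SD of at most 19.15, and the quoted medians and quartiles do not establish that.

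For a 4-point difference with 360 analysed per group, power ranges from about 50% to 90% across the shapes tried. The corresponding detectable differences run from about 3.4 to 5.7 points. The normal, uniform and capped-normal cases all fall below 80%, the last two only slightly. This does not show that the study is underpowered; it shows that 360 cannot be called conservative. The figures rest on the plan's 4 points, an unadjusted comparison and, for the bounded shapes, an assumed lowest score. The non-consent shortfall is a smaller, separate matter: 77.5% in place of 80% at the upper end of the plan's own allowance.

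**What to change.** Amend the wording of Protocol 7.5 and SAP 1.1.2:

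1. Remove the statement that quartile distances serve as SDs, and delete *conservatively*.
2. State the condition and the sensitivity, naming the shape beside each figure. For example:

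> The source reports only medians and quartiles, so the SD is not known. With 360 analysed per group, 80% power for 4 points requires a pooled SD of at most 19.15. Normal theory (SD = IQR/1.35, pooled 24.8, ignoring the ceiling at 100) gives about 58% power; a uniform shape, 79%; a normal capped at 100, 76%. Scores spread evenly between the quartiles within 0–100 give about 50% to 90% for an assumed lowest score of 0 to 50. The difference detectable with 80% power is about 3.4 to 5.7 points.

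3. Say that these figures are for an unadjusted two-group comparison, before any loss from matching under SAP 7.2.3.1.
4. Say that 420 identified per group covers about 14% non-consent, and that at 20% 336 remain (77.5% power at SD 19.1).

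The cost is text in two documents. Enrolment, data collection and analysis stay as they are; the stated power becomes a range instead of one figure.

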7.6. Data management

7.6.1. Data collection

As used in this study protocol, the term case report form should be considered a paper document record in accordance with the data collection method used in this study. A case report form should be prepared for each patient included in the study. The original case record form should not be disclosed in any form to Pfizer's authorized representative or any third party except the regulatory authority without the written consent of Pfizer.

The investigators should collect and report all clinical and laboratory data entered in the case report form and other data collection forms (evidence documents). And the researcher have ultimate responsibility for ensuring their accuracy, authenticity / originality, attributability, completeness, consistency, readability, timely collection (concurrency), continuity and, where necessary, availability. In order to verify accuracy of the information contained in the case record, the case report form should be signed by the researcher or a delegated researcher. All modifications to the case report form and the grounds document should include the date and initials, the reason (if necessary), and do not cover the original content.

In most cases, the supporting documentation is the patient's medical chart record. In this case, the data collected in the case report form should match the data recorded in the chart.

In some cases, the case report form or part of the case report form may also be the evidence document. In this case, the document should be kept in the investigator's center and Pfizer, and clearly stated in the documentation that the case report form, along with the data recorded in the case report form, is the basis document.

7.6.2. Data collection method

Data will be collected based on the study timeline. The study will be conducted at a total of 23 institutions from the start date until March 31, 2020 according to the treatment timelines in patients with RA. Patients who satisfy inclusion and exclusion criteria and voluntarily consent to participate in the study will be enrolled. Patient information will be retrieved from medical charts. Information that cannot be obtained from medical charts will be collected from patient

questionnaires, and treatment satisfaction and quality of life will be self-reported using authorized tools (TSQM and EQ-5D-3L).

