7. RESEARCH METHODS

7.1. Study design

This study is a multi-center, non-interventional cross-sectional study.

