7.7. Data analysis

Data analysis will be undertaken using SAS software, version 9.4 of the SAS® system for Windows (Cary, NC, USA).

Detailed methodology for summary and statistical analyses of data collected in this study will be documented in a Statistical Analysis Plan, which will be dated, filed and maintained by the sponsor. The Statistical Analysis Plan may modify the plans outlined in the protocol; any major modifications of primary endpoint definitions or their analyses would be reflected in a protocol amendment.

The subjects of this study are as follows.

- All patients enrolled as study subjects who were eligible for two treatment groups.

The general principles of statistical analysis in this study are as follows:

- Complete statistical analysis plan before DB lock is done. The details of the data analysis methodology of this study are specified in the statistical analysis plan.
- If a statistical test is required, it should be carried out at the two-side significant level 5%.
- When multivariable analysis is performed, independent variables used for actual analysis can be added or subtracted considering the structure of collected data and general characteristics of study subjects.
- In the case of data that do not have a bias in the interpretation of the results, the analysis is carried out based on only the observed data without adjusting the missing values. If it is deemed that significant bias is imposed on the interpretation of the results when the analysis is carried out with only the observed data, the analysis is carried out by statistically adjusting the missing values using the following appropriate missing value imputation method. As a method of replacing missing values, methods such as mean imputation, me

dian imputation, probability imputation, regression imputation, ratio imputation, or multiple imputation are used depending on the pattern of missing values.

- Other inconsistent data may be excluded from the analysis under the responsibility of the investigator.

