#### 7.2.4 Summary of Analyses

Outcome	Analysis Set	Subgroups	Statistical Method	Covariates/Strata	Missing Data
Treatment satisfaction	FAS	Not Applicable	Multivariate linear regression analysis	Demographics and treatment pattern variables	After reviewing the data, substitute with the multiple imputation (MI) method. However, covariates that do not affect the results will not be

PFIZER CONFIDENTIAL

					substituted.
EQ-5D index	FAS	Not Applicable	Multivariate linear regression analysis	Demographics and treatment pattern variables	After reviewing the data, substitute with the MI method. However, covariates that do not affect the results will not be substituted.
EQ VAS	FAS	Not Applicable	Multivariate linear regression analysis	Demographics and treatment pattern variables	After reviewing the data, substitute with the MI method. However, covariates that do not affect the results will not be substituted.

PFIZER CONFIDENTIAL

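### Institution is not specified in the propensity model, the outcome models or the standard errors of a non-randomised comparison across 23 institutions

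*Protocol*

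**What the plan says.** Protocol 7.1 describes the design: "This study is a multi-center, non-interventional cross-sectional study". Protocol 7.6.2 gives the number of sites: "The study will be conducted at a total of 23 institutions". Protocol 7.5 plans that "approximately 420 subjects will be identified from each group from the total of 840 subjects in this study".

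- **Propensity model (SAP 7.2.3.1):** scores use subjects' "demographic and clinical characteristics as covariates".
- **Covariate table (SAP 5.4):** it lists more than 30 items, down to the type, number, dose and duration of each class of concomitant drug. Institution, region and physician are not among them.
- **Outcome models (SAP 7.2.4):** linear regression for all three outcomes, with covariates given as "Demographics and treatment pattern variables".
- **Matched data (SAP 3.2, 7.1.1, 7.1.2, 7.2.3.2):** paired t-test, Wilcoxon signed-rank test, McNemar's test, conditional logistic regression or a linear mixed model, chosen because the data are matched. No site random effect is named.
- **Flexibility (Protocol 7.7, SAP 3.2):** independent variables may be added or dropped in light of the data.

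Neither document mentions a site effect, within-site matching, cluster-robust errors, an ICC or a design effect. The sample size formula in Protocol 7.5 treats patients as independent.

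**The concern.** SAP 7.2.3.1 justifies propensity scores on the ground that a covariate which steers patients towards one treatment can distort the comparison. Where a patient is treated is a natural candidate: hospitals may differ in how readily they use each drug, and also in how satisfied their patients are. If the two go together, part of the difference between hospitals is read as a difference between drugs.

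There is a second consequence even without that link. If drug share varies between hospitals and outcomes within a hospital are correlated, the ordinary standard error understates the uncertainty. Confidence intervals are then too narrow and 5% tests reject too often.

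Protocol 7.9 acknowledges only confounders that were not measured. Institution is a grouping the study holds, so it could be handled by design of the analysis.

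**Working it through.** **Inputs from the documents.** 23 institutions (Protocol 7.6.2); 420 per group, 840 in total; TSQM target difference 4; pooled SD 14.58 (smallest) or 19.1 (largest); two-sided 5%; 80% power (Protocol 7.5 and 7.7).

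**Assumptions not in the documents.** Outcome ICC ρ = 0.02–0.05; between-site SD of the share on tofacitinib, s = 0.1–0.3; correlation r between a site's share and its mean satisfaction; equal-sized sites; no covariate adjustment.

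**The plan's own figure.** n = 2 × 19.1² × (1.96 + 0.842)² / 4² = 358.02, rounded up to the stated 359. With SD 14.58 it is 208.62, or 209 as stated. These reproduce, under independence.

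**Standard error.** Let m = 840/23 = 36.5 patients per site. The variance of the difference in means is SD² × [(1 − ρ)(1/n₁ + 1/n₀) + ρ Σ(n₁ⱼ/n₁ − n₀ⱼ/n₀)²]. With equal sites and an overall 1:1 split, dividing by the independent-patient variance gives

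ratio = 1 − ρ + ρ × 4m × s², with 4m = 146.1.

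True level = 2 × [1 − Φ(1.96/√ratio)]. Power = Φ(4/(19.1 × √(2/420 × ratio)) − 1.96), which is 85.9% at ratio 1.

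| ρ | s | ratio | true level | power, SD 19.1 |
|---|---|---|---|---|
| 0.02 | 0 | 0.98 | 4.8% | 87% |
| 0.05 | 0 | 0.95 | 4.4% | 88% |
| 0.02 | 0.2 | 1.10 | 6.1% | 83% |
| 0.02 | 0.3 | 1.24 | 7.9% | 78% |
| 0.05 | 0.2 | 1.24 | 7.9% | 78% |
| 0.05 | 0.3 | 1.61 | 12.2% | 67% |

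The ratio equals 1 when 4m × s² = 1, that is s = 1/√146.1 = 0.083. This is also the spread expected by chance if each patient had a 50% probability of either drug: √(0.25/36.5) = 0.083. So the naive error is too small only when drug share varies between sites by more than chance.

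**Smaller sites.** With the 720 patients required rather than 840, m = 720/23 = 31.3 and 4m = 125.2. At ρ = 0.05, s = 0.3 the ratio is 0.95 + 0.05 × 125.2 × 0.09 = 1.51 and the true level 11.1%.

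**Bias.** Bias = r × s × √ρ × SD / 0.25, where 0.25 is the variance of a 1:1 treatment indicator. With ρ = 0.05:

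- r = 0.3, s = 0.1, SD 14.58: 0.3 × 0.1 × 0.2236 × 14.58 / 0.25 = 0.39 points.
- r = 0.3, s = 0.1, SD 19.1: 0.51 points.
- r = 0.5, s = 0.2, SD 14.58: 1.30 points.
- r = 0.5, s = 0.2, SD 19.1: 1.71 points.
- r = 0: zero.

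**Simulation check.** With 23 sites of 37 patients, SD 19.1, no true effect, ρ = 0.05 and s = 0.2, the unadjusted test rejected 7.7% of the time at r = 0. At r = 0.3 and 0.5 the spurious difference was 1.0 and 1.6 points, with rejection in 15% and 27%. Institution fixed effects brought the bias to about zero and rejection to 4.5–5.9%. The estimate's SD was 1.42–1.44, against 1.47–1.51 without them.

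**The case against.** **The plan leaves room.** The clause on adding independent variables could admit institution. It commits to nothing, however, and an added covariate does not supply clustered errors for the matched or weighted analyses.

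**The matched methods do allow for dependence.** A reader might infer that every planned test treats patients as independent. That is not so: the paired tests and the linear mixed model allow for correlation within matched sets. What stands is narrower: none of them allows for correlation within a hospital.

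**The effect may be nil.** This stands. Site confounding needs drug share and satisfaction both to vary by site and to be correlated, and the documents report none of these. With an identical drug mix everywhere, the variance ratio is 0.90–0.99 for ICC 0.01–0.10, so the naive error is slightly conservative.

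**The figures are for an unadjusted difference.** This stands too. The plan adjusts for education, finances, employment, disease activity and prior and concomitant drugs, which may absorb part of the difference between sites.

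**Site size.** Protocol 7.5 says "Considering 10–20% of subjects not consenting, the actual sample size would be 400–450 subjects per group", so 36.5 per site may be too high. Using 31.3 lowers the figures a little, as shown.

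**Is institution available?** Protocol Table 1 does not list it, and the central data are coded. But each site holds its own code list (Protocol 8.1) and data queries go back to each institution (7.6.3), so the grouping should be recoverable.

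**The study is not confirmatory.** SAP 3.1 declares no hypothesis and Protocol 7.9 disclaims causal proof. That makes the error rate less decisive, but the interval and the adjusted difference are still the main results.

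**Conclusion.** The omission holds in all three places: propensity model, outcome models and standard errors. The consequence is potential, not demonstrated. A reader might infer that the comparison is confounded by hospital, or that its standard errors are certainly too small. The documents support neither, because they give no ICC and no drug mix by site, and an even mix would push the error the other way.

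Under the stated assumptions (unadjusted difference, equal sites), a nominal 5% test has a true level of about 6–12% for ICC 0.02–0.05 and share SD 0.2–0.3. Bias is about 0.4–1.7 TSQM points for ICC 0.05, share SD 0.1–0.2 and correlation 0.3–0.5, which is roughly 10–43% of the 4-point target (0.4/4 to 1.7/4). Confidence is high in the omission and low in the size. As written, the plan would not reveal which case applies, and a cheap correction exists, so the SAP should be changed.

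**What to change.** 1. Add institution to SAP 5.4 and confirm that the site identifier reaches the analysis file.
2. In SAP 7.2.3.2 to 7.2.4, fit the outcome regressions with institution fixed effects, pooling very small sites by a rule set in advance. Alternatively, use a random institution intercept and include the site's drug share as a covariate. A random intercept alone removes site confounding only in part.
3. For the matched and IPTW analyses, use institution-clustered standard errors with a small-sample correction for 23 clusters. These correct the uncertainty but remove no confounding.
4. Report drug share by institution, and the estimated ICC.
5. As a sensitivity analysis where overlap allows, match within institution or put institution in the propensity model.

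**Cost.** SAP wording and some programming; no new data collection is expected. Single-drug sites contribute little to a within-site contrast, and intervals may widen. Institution in the propensity model can produce extreme weights or more unmatched patients, and so could trigger the 25% rule in SAP 7.2.3.1. That is why step 5 should remain a sensitivity analysis.
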